12.3 Standardization of Anti-arrhythmic Drug Use during Follow-up Period

Postoperative use of anti-arrhythmic drugs (AAD) following atrial fibrillation surgery varies significantly among sites and among clinicians at individual sites. In addition, regulation of the medical regimen may be under the direction of the surgeon, the referring clinical cardiologist or both in collaboration. Since no specific data are available to prove efficacy of any given approach, this shall be left up to the discretion and ordinary practice of the investigators. This will not influence the primary efficacy outcomes analysis, since efficacy will be evaluated after AAD washout.

The presence or absence of atrial fibrillation shall be assessed in each treatment subject	

In addition, some subjects may present for medical care between or at scheduled visits, at which time AF may be discovered. If a patient is in AF during the follow-up course, additional attempts at medical management and cardioversion/catheter ablation can be undertaken as medically indicated. However, every effort should be made to discontinue AADs at least 4 weeks (except amiodarone which must be discontinued 12 weeks prior to assessment) prior to the Holter, Zio™ Patch or PPM interrogation evaluations ... If AADs cannot be discontinued at least four (4) weeks (12 weeks for amiodarone) the subject will, by definition not be considered a primary efficacy outcome success.

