The proportion of patients free from AF (i.e. no episodes lasting > 30 continuous seconds duration of either Atrial Fibrillation, Atrial Flutter or Atrial Tachycardia) while off Class I and III antiarrhythmic drugs for at least 4 weeks (except amiodarone which must be 12 weeks prior to assessment), as determined by an independent core lab assessment of 48 hour Holter, Zio[™] Patch or PPM interrogation recording performed at a minimum of 12, 24 and 36 months postoperatively (hypothesis test at 36 months).

Primary Safety
Outcome:

[figure not shown]
The proportion of patients with any serious device or ablation procedure-related adverse events
 within 30 days post-procedure or hospital discharge (whichever is later) as adjudicated by a Clinical Events Committee.

Secondary Efficacy Outcome:

The proportion of patients free from AF, regardless of AAD usage (i.e. no episodes lasting > 30 continuous seconds duration of either Atrial Fibrillation, Atrial Flutter or Atrial Tachycardia), as determined by an independent core lab assessment of 48 hour Holter, Zio™ Patch or PPM interrogation recording performed at a minimum of 12, 24 and 36 months postoperatively.

Secondary Safety Outcomes:

- Composite major adverse event: Serious adverse events occurring post-operatively within 30 days post-procedure or hospital discharge (whichever is later) including:
 - Death (includes deaths after 30 days or hospital discharge if death is procedure related).
 - Stroke (resulting in significant permanent disability)
 - o TIA
 - Myocardial infarction, and
 - Excessive bleeding (requiring >2 units of blood replacement and surgical intervention).

 Pacemaker implantation (PPM) within 30 days post procedure will be summarized and reported by reason for PPM (i.e., sinus node dysfunction, AV-node, etc.).

Planned Enrollment:

Up to 390 subjects.

Population:

Subjects who have non-paroxysmal forms of AF and are scheduled to undergo a primary open cardiac surgical procedure requiring cardiopulmonary bypass including valve surgery and/or CABG.

Follow-up Schedule: All patients will undergo clinical follow-up in hospital and at 30 days,

4, 12, 24 and 36 months post procedure.

Number of Sites: 50 study centers located in North America

Study Duration Study Start: Q3/2012

(Estimated): Enrollment Completion: Q4/2014 Follow Up Completion: Q4/2017

Final Report: Q2/2018 (See detail in section 6.5)

Inclusion Criteria:

[figure not shown]
• Age ≥ 18 years.

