12.1 Repeat Ablation and/or Cardioversion Procedures

All information regarding any repeat catheter ablations (reason for the re-do as well as location) or any cardioversions will be collected and documented in the CRF. The most prevalent post-procedure rhythm will also be documented and recorded in the CRF.

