13.3 Events that do not require reporting to the sponsor

For purposes of this study, the following events will not be required to be reported as adverse events to the sponsor, because they are normally expected to occur in conjunction with surgical treatment for non-paroxysmal forms of atrial fibrillation procedures (Maze IV) or are associated with customary, standard care of patients undergoing cardiac surgery:

- Chest pain without associated ECG changes
- Post-operative pain
- Post-anesthesia emesis, nausea, or headache (within 24 hours of procedure)
- Electrolyte imbalance without clinical sequelae following procedure, even if requiring correction
- Pre planned future surgical procedures
- Low grade temperature increase (101°F or 38.5°C)
- Dizziness: Imprecise term commonly used to describe various symptoms such as faintness, giddiness, imbalance, lightheadedness, unsteadiness or vertigo.
- Elevated white blood count, outside the standard laboratory normal value, without signs and symptoms of infection
- Post-operative hematocrit decrease from baseline measured in the OR, prior to the first incision, not associated with hemodynamic changes, remaining above 25% and requiring < 3 units PRBC's
- Minor, localized tenderness, swelling, induration, oozing, etc. at surgical site.
- Sinus bradycardia/tachycardia that does not require treatment or intervention
- Systolic or diastolic blood pressure changes that do not require treatment or intervention.
- Any blood transfusions during preplanned operative procedures and unrelated to an adverse event.
- Thrombocytopenia: does not become an AE until treatment is administered.
- Atelectasis collapse of lung tissue affecting part or all of one lung; the alveoli are deflated. This
 is not considered to be an AE unless treatment other than chest PT is required or it prolongs
 hospitalization.
- Hyperglycemia The use of insulin in the post-operative period does not constitute
 hyperglycemia if during the same hospitalization. An elevated blood sugar of less than 250
 mg/dl during the first 48 hours post-operative does not constitute hyperglycemia.
- Pleural effusion is not an event unless treatment with thoracentesis or chest tube insertion is required
- Pericardial effusion without hemodynamic compromise or treatment

Atrial Fibrillation / Atrial Flutter / Atrial Tachycardia with or without cardioversion. Note: the
occurrence of AF is reported as an outcome in the study and documented on a follow up visit
CRF.

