16.6 Statistical Analyses

Primary Analysis

Serious device and ablation procedure related AE rates and confidence intervals will be summarized at discharge, 30 days, and 1-year with a hypothesis test performed on the cumulative 30 day serious device

and ablation procedure related AE rate. The primary safety hypothesis test will be conducted using a one-sided exact binomial test for proportions at the 0.05 overall level of significance.

The efficacy outcome rate of freedom from AF, off antiarrhythmic drugs along with confidence intervals will be summarized at 1, 2 and 3 years (i.e. 12. 24, 36 month follow-up), with a hypothesis test performed on the 3-year success outcome. The primary efficacy hypothesis test will be conducted using a one-sided exact binomial test for proportions at the 0.05 overall level of significance.

Secondary Analysis

Secondary outcomes will be summarized for the analysis population and certain sub-populations. Two-sided 95% confidence intervals will be calculated for all presented rates. Descriptive analyses will be provided for patient demographics, clinical device/procedural success, medical histories, and comorbidities. Logistic regression analyses may be used to screen a wide range of parameters for their association with some outcomes.

Procedures to Account for Missing Data

Reasonable efforts will be made to obtain complete data for all patients; however, missing observations will occur due to patients lost to follow-up or noncompliance with required assessments. The reasons for missing data will be evaluated (e.g. patient is deceased, lost to follow up, missed visit, etc.). In addition, the distribution of prognostic factors between patients with data and those without data will be examined to evaluate any potential sources of bias.

Any missing observations will be described in detail and evaluated for assessment of possible bias. For the primary analysis of safety and efficacy outcomes, missing data will be imputed using multiple imputation methods (e.g. SAS PROC MI). Additional sensitivity analyses of missing data including 1) considering everyone who was a failure at last visit also a failure at 3 years and multiple imputation on everyone who was a success at last visit, 2) including everyone LTFU as a failure and 3) a tipping point analysis will also be performed.

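### On the visible text, a patient retreated after the index procedure who has a clear, drug-free 36-month recording counts as an efficacy success, and no visible analysis separates such patients

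*Combined protocol and SAP*

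**What the plan says.** The Protocol Summary gives the primary efficacy outcome without a break. It sets two conditions. The core-lab recording must show no fibrillation, flutter or atrial tachycardia beyond 30 seconds, and this must hold "while off Class I and III antiarrhythmic drugs for at least 4 weeks (except amiodarone which must be 12 weeks prior to assessment". The recording is "performed at a minimum of 12, 24 and 36 months postoperatively (hypothesis test at 36 months". Section 7.1 repeats this as far as it can be read. The secondary efficacy outcome (7.2) drops the drug condition and is otherwise the same.

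Section 12.3 expects that "some subjects may present for medical care between or at scheduled visits, at which time AF may be discovered" and says that, for a patient in AF, "additional attempts at medical management and cardioversion/catheter ablation can be undertaken as medically indicated". If the drugs cannot be stopped in time, "the subject will, by definition not be considered a primary efficacy outcome success".

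Section 12.1 provides, for the case report form, that "All information regarding any repeat catheter ablations (reason for the re-do as well as location) or any cardioversions will be collected and documented"; it names no analysis that uses these data. Section 13.3 exempts AF, cardioverted or not, from adverse event reporting, on the ground that the "occurrence of AF is reported as an outcome in the study and documented on a follow up visit" form.

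Section 16.6 plans yearly rates "with a hypothesis test performed on the 3-year success outcome". Its listed sensitivity analyses all stand under the missing-data heading. Section 5.0 says efficacy will be shown by establishing that the device eliminates non-paroxysmal AF.

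**The concern.** The study has one arm, so no control group shows how much of the 36-month rate is owed to later procedures. Section 12.3 argues that varying AAD practice will not affect the primary analysis because efficacy is judged after washout. An ablation cannot be washed out. If AF recurs, is re-ablated, and the 36-month recording is clear, the visible rule credits that result to the treatment under study. What is at stake is the reading of the 36-month rate: whether it describes the index procedure alone, or the index procedure plus whatever followed.

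**Working it through.** **Step 1. Follow a retreated patient through the visible rules.** Suppose AF recurs after the index procedure, the patient has a catheter ablation, and the 36-month recording is clear with the drug-free interval met.

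- Protocol Summary: both conditions are met, and retreatment is not mentioned.
- 12.3: the procedure is permitted; the only non-success rule visible concerns AADs.
- 12.1: the procedure is recorded.
- 13.3: the AF is captured as an outcome on the visit form, but is not made a primary-endpoint failure.
- 16.2: stratification is by type of surgery and by new or existing user, not by retreatment.
- 16.6: the three sensitivity analyses are carrying a last-visit failure forward to 3 years, counting those lost to follow-up as failures, and a tipping point. All handle missing outcomes. This patient's outcome is observed, so none applies.

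The patient is a success.

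**Step 2. Test the cumulative reading.** If success requires clear recordings at 12, 24 and 36 months, AF on the 12- or 24-month recording already fails the patient. AF discovered and treated between recordings, which 12.3 foresees, still escapes. The stated 36-month test and the separate yearly rates in 16.6 fit the visit-specific reading but do not settle it.

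**Step 3. Arithmetic of size.** Inputs from the documents: 57.8% success from 26/45 (16.5); more than 275 subjects at 3 years (16.3); 250 evaluable in the attrition scenario (16.5). The plan's rate reproduces: 26/45 = 0.578. The efficacy goal and power cannot be read, so the efficacy power statement cannot be reproduced.

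Weight of one patient: 1/275 = 0.36 points (at most, since 16.3 expects more than 275); 1/250 = 0.40 points.

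With N = 275 and S = 0.578 × 275 ≈ 159 successes, recounting k patients who succeeded only after retreatment gives (S − k)/N. The values of k are assumptions; the documents give no retreatment rate.

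| k (share of 275) | Rate |
|---|---|
| 0 | 159/275 = 57.8% |
| 3 (1.1%) | 156/275 = 56.7% |
| 6 (2.2%) | 153/275 = 55.6% |
| 11 (4.0%) | 148/275 = 53.8% |
| 28 (10.2%) | 131/275 = 47.6% |

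These are complete-case figures; the plan multiply imputes missing outcomes.

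**Step 4. The reference side.** The documents do not say how retreated patients were counted among the 26 successes. One patient there is worth 1/45 = 2.2 points (25/45 = 55.6%).

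**The case against.** The strongest objection is that text is hidden where a rule would sit. Section 7.1 breaks off, 12.3 has gaps in the relevant paragraph, the efficacy hypotheses in 16.5 cannot be read, and 16.2 defers other sub-populations to a SAP that is not visible. This stands as a limit: a reader might infer that the plan has no rule, and the documents support only that none is visible. It does not remove the point, because the Protocol Summary definition is complete and the list of sensitivity analyses in 16.6 shows no gap.

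A reader might also infer that the plan is inconsistent, disqualifying drugs but not procedures. That is too strong. The AAD rule is a washout at assessment: a patient treated with AADs earlier who stops in time can still succeed. Neither kind of earlier treatment visibly disqualifies. The remaining difference is that an ablation cannot be withdrawn before the recording.

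Third, rhythm status at 36 months under ordinary care is a legitimate target for an observational study of commercial use. This stands, and it is why the primary test should not change.

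Last, the retreatment data are collected, so the estimate could be produced later. True, but the classification rule would then be chosen after the data were seen.

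**Conclusion.** The point holds in limited form. On the visible text, the 36-month rate can include success due to a later ablation or cardioversion, and no visible analysis shows how much. On a cumulative reading, only AF found and treated between recordings is affected.

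The size is unknown. The table assumes shares from 0% to about 10%, and nothing in the documents anchors that range. A reader might infer that the primary test is biased towards passing, or that the comparison with the 57.8% reference is inflated. Neither is supported: no efficacy goal is visible, and the handling of retreatment in the 26/45 is not stated, so even the net direction against the reference is open. This is a cheap improvement to interpretation. It does not show that the primary analysis is wrong.

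**What to change.** Keep the primary outcome and test unchanged; nothing here touches patient care. Add to 16.6:

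1. One supporting 36-month estimate with a two-sided 95% confidence interval and no formal test, counting as non-success any patient with a repeat ablation for AF, flutter or atrial tachycardia at any time after the index procedure.
2. A second row that also counts as non-success any patient cardioverted between the 24- and 36-month recordings.
3. A table of retreatments by type and timing, from the 12.1 CRF data.

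If text not visible here already provides any of this, a cross-reference is enough.

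The cost is one derived variable and one table, and a supporting rate that may be less favourable. Section 12.1 names repeat catheter ablations and cardioversions but not surgical re-ablation, so check that the CRF captures the latter.

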13.0 ASSESSMENT OF SAFETY

13.1 Adverse Events

During each clinical follow-up, the investigator or designee will determine adverse event (AE) occurrences. An adverse event is any untoward medical occurrence (signs, symptoms, abnormal laboratory findings) in a patient regardless of relationship to the device or procedure. Each adverse event is considered to be either anticipated or unanticipated as described below. The site is required to report all adverse events that occur in the study.

13.2 Anticipated Adverse Events

A variety of complications are expected to occur in subjects undergoing treatment for atrial fibrillation with the AtriCure Synergy Ablation System concomitant with an open-heart procedure requiring cardiopulmonary bypass. These anticipated adverse events are provided in Appendix A.

These events shall also be classified according to the suspected causality by the study investigator. Causality can be attributed to the device, the surgical procedure or to the subject's underlying disease according to the definitions below.

Device Related Adverse Event: An adverse event, which in the judgment of the Investigator, results from use of the AtriCure Synergy Ablation System.

Ablation Procedure Related Adverse Event: An adverse event which, in the judgment of the Investigator, results as a consequence of the ablation procedure and is not specifically related to use of the AtriCure Synergy Ablation System.

Surgical Procedure Related Adverse Event: An adverse event which, in the judgment of the Investigator, results as a consequence of the surgical procedure to address underlying structural heart disease and is not specifically related to use of the AtriCure Synergy Ablation System or the ablation procedure.

Underlying Disease Related Adverse Event: An adverse event which, in the judgment of the Investigator, results as a consequence of the subject's underlying medical condition and is related to neither the ablation nor structural heart disease surgical procedures nor to use of the AtriCure Synergy Ablation System.

If the Investigator cannot determine the cause of the event, it should be classified as unknown.

13.3 Events that do not require reporting to the sponsor

For purposes of this study, the following events will not be required to be reported as adverse events to the sponsor, because they are normally expected to occur in conjunction with surgical treatment for non-paroxysmal forms of atrial fibrillation procedures (Maze IV) or are associated with customary, standard care of patients undergoing cardiac surgery:

- Chest pain without associated ECG changes
- Post-operative pain
- Post-anesthesia emesis, nausea, or headache (within 24 hours of procedure)
- Electrolyte imbalance without clinical sequelae following procedure, even if requiring correction
- Pre planned future surgical procedures
- Low grade temperature increase (101°F or 38.5°C)
- Dizziness: Imprecise term commonly used to describe various symptoms such as faintness, giddiness, imbalance, lightheadedness, unsteadiness or vertigo.
- Elevated white blood count, outside the standard laboratory normal value, without signs and symptoms of infection
- Post-operative hematocrit decrease from baseline measured in the OR, prior to the first incision, not associated with hemodynamic changes, remaining above 25% and requiring < 3 units PRBC's
- Minor, localized tenderness, swelling, induration, oozing, etc. at surgical site.
- Sinus bradycardia/tachycardia that does not require treatment or intervention
- Systolic or diastolic blood pressure changes that do not require treatment or intervention.
- Any blood transfusions during preplanned operative procedures and unrelated to an adverse event.
- Thrombocytopenia: does not become an AE until treatment is administered.
- Atelectasis collapse of lung tissue affecting part or all of one lung; the alveoli are deflated. This
 is not considered to be an AE unless treatment other than chest PT is required or it prolongs
 hospitalization.
- Hyperglycemia The use of insulin in the post-operative period does not constitute
 hyperglycemia if during the same hospitalization. An elevated blood sugar of less than 250
 mg/dl during the first 48 hours post-operative does not constitute hyperglycemia.
- Pleural effusion is not an event unless treatment with thoracentesis or chest tube insertion is required
- Pericardial effusion without hemodynamic compromise or treatment

Atrial Fibrillation / Atrial Flutter / Atrial Tachycardia with or without cardioversion. Note: the
occurrence of AF is reported as an outcome in the study and documented on a follow up visit
CRF.

13.4 Serious Adverse Events

All SAEs must be reported to AtriCure or designee within 24 hours of investigational site knowledge of
the event.

A serious adverse event (SAE) is any untoward medical occurrence that:

- Results in death
- Is life-threatening
- Requires inpatient hospitalization or prolongation of existing hospitalization
- Results in persistent or significant disability/incapacity, or
- Is an important medical event which may jeopardize the subject and may require medical or surgical intervention to prevent one of the above outcomes

The Investigator at each participating center is ultimately responsible for reporting adverse events (complications) to AtriCure or its designated CRO. Investigators must report SAEs within 24 hours of investigational site knowledge of event occurrence by entering data into the Case Report Form in the electronic database. The Investigator is required to complete the adverse event Case Report Forms at each study visit, if an adverse event occurs. One adverse event CRF must be completed for each adverse event.

All adverse events will be reported to FDA at least annually.

14.0 Clinical Events Committee (CEC)

[figure not shown]
An independent group of physicians that are not involved in the clinical investigations will act as the Clinical Events Committee (CEC) under the direction of The CEC will be responsible for the review and validation of reported potential ENDPOINT adverse events (i.e.: all device/procedure related SAEs) that occur within 30 days post procedure per the CEC Charter. The CEC shall classify each of these adverse events based on severity and association to the device and/or procedure. During the review of the events, the CEC will be blinded to the clinical site as much as possible. The CEC Charter will be developed prior to the start of study enrollment. This charter shall include consistent definitions for each type of event and shall outline the review process.

15.0 MEDICAL DEVICE REPORTING

15.1 Manufacturer Reporting Requirements

The AtriCure Synergy Ablation System is commercially available and subject to FDA Medical Device Reporting (MDR) regulations. These regulations require manufacturers who receive complaints of device malfunctions, serious injuries or deaths associated with medical devices to notify FDA of the incident. AtriCure will comply with the MDR requirements for devices used in this study through the information gathered on the case report forms and source documents obtained from the site. If there is a device malfunction or other observation, the Device Observation CRF requires the Investigator to notify AtriCure immediately and indicate if the observation resulted in an adverse events and indicate if complications are related to the device, procedure or underlying disease. The collective information required on AtriCure MDR procedure forms are designed to comply with time sensitive reporting requirements. AtriCure will submit MDR reports according to 21 CRF parts 803.50 through 803.58.

In the event of an MDR, the site should contact:

